3.2. Stratified Analysis

There are two stratification variables for randomization: oral CS use at baseline (yes or no), and diagnosis of recurrent idiopathic pericarditis at RI baseline (yes or no). When an analysis is to be stratified by these variables and a stratum has ≤ 5 events of interest in a log-rank test or the same response in all subjects in a CMH test, the strata for diagnosis of recurrent idiopathic pericarditis will be pooled. If the same situation still exists, the analysis will be done without stratification.

3.3. Testing Hypotheses and Multiplicity Adjustment

All statistical tests for the treatment comparison of efficacy endpoints in the RW period will be based on a 1-sided $\alpha=0.025$. For each endpoint, the null hypothesis is that the effects of riloncept and placebo are the same. The alternative hypothesis is that riloncept is better than the placebo.

In order to control the overall 1-sided type I error rate at the 0.025 level, a gatekeeping procedure in combination with Hochberg's procedure will be applied to testing the primary and major secondary endpoints. If the 1-sided p-value for testing the primary endpoint is ≤ 0.025 , a significant treatment effect on the primary endpoint will be claimed.

Section 5.2.2.1 provides the order of major secondary endpoints. If the primary endpoint is significant, the first major secondary endpoint, i.e., proportion of subjects who maintained clinical response at Week 16 of RW period will be tested at 1-sided $\alpha=0.025$. A significant treatment effect on this major secondary endpoint will be claimed if the 1-sided p-value is ≤ 0.025 . If the treatment effect is not significant on the primary endpoint, significance on this major secondary endpoint cannot be claimed regardless of the result.

If both primary and first major secondary endpoints are significant following the above procedure, the second and third major secondary endpoints defined in Section 5.2.2.1 will be tested with Hochberg's procedure at overall 1-sided $\alpha=0.025$. If both 1-sided unadjusted p-values are ≤ 0.025 , claim significance of riloncept for both endpoints. If the larger 1-sided p-value is > 0.025 , compare the smaller 1-sided p-value with 0.0125. If the smaller 1-sided p-value is ≤ 0.0125 , claim significance of riloncept on this endpoint.

3.4. Subgroups to be Analyzed

Subgroup analyses for the primary efficacy endpoint will be performed by the following variables for the RW period:

- Oral CS use at baseline (RI baseline, i.e., beginning of RI period): yes or no
- Diagnosis of recurrent idiopathic pericarditis (RI baseline): yes or no
- Age group: 12 - <18, 18 - <65, and 65 – (maximum age in ITT analysis set)
[Analysis for the pediatric group (12- <18) may not be performed if the sample size is too small.]
- Gender: males vs. females
- Race: Caucasian vs. non-Caucasian
- Region: USA vs. non-USA
- Number of pericarditis episodes at enrollment (including index and qualifying episodes): < 5 vs. ≥ 5

- ADA status: ADA positive at any assessment, ADA positive with neutralizing antibody at any assessment, and ADA negative at every assessment.

P-values and summary statistics will be generated following Section 5.2, with the understanding that the sample size is likely too small to have an adequate power. The forest plot with 95% CI will be provided for the primary efficacy endpoint.

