8. ANTI-RILONACEPT ANTIBODIES

Blood sample for testing anti-rilonacept antibody (ADA) will be collected at RI baseline, RI weeks 2, 6, 12 (= RW baseline), RW week 24, end of RW/LTE baseline, and LTE week 24. ADA status will be categorized as follows.

1. Treatment-emergent ADA, including treatment induced or boosted [increased by one quartile (with all titers collected) from the previous assessment]
2. Prior existing ADA (without treatment boosted)
3. ADA negative at every assessment.

For subjects with treatment-emergent ADA, the maximum post-baseline titer level (low, medium, high) will be summarized. The 3 levels (low, medium, high) will be divided based on 25th and 75th percentiles from all ADA titers pooled.

The following endpoints will be summarized for each category of ADA status above:

- Number and percentage of subjects with injection site reactions within 24 hours of administration
- Subjects with Neutralizing antibody in the first 2 categories above.

A summary table will be provided for number and percent of subjects with positive or negative anti-rilonacept antibody by visit. Individual's ADA status and titer level (if positive) at each visit will be provided.

The number and percent of subjects with anti-rilonacept-antibody positive at any visit vs. those with negative at every visit will also be provided. The summary statistics of CRP and NRS level will be provided for these 2 subsets of subjects at each visit by study period, and by treatment arm in the RW period (before vs. after receiving bailout rilonacept and overall).

The following 3 categories will be used in the subgroup analysis for the primary endpoint, Summary of NRS scores and CRP levels over time, summary of TEAEs (overall and drug related), and blood concentration over time:

1. Subjects with ADA Positive at Any Assessment
2. Subjects with ADA Positive and Neutralizing Antibody at Any Assessment
3. Subjects with ADA Negative at Every Assessment

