b Scheduling of visits within visit windows requires cautious planning to ensure there is no interruption to subject evaluation and study drug treatment.

c Full physical examination includes at minimum evaluation of vital signs, head, eye, ear, nose, and throat as well as cardiovascular, dermatological, musculoskeletal, respiratory, GI, genitourinary, and neurological systems. The decision to perform examination of genitourinary system should be guided by clinical judgement.

Statistical Analysis Plan

Kiniksa Pharmaceuticals, Ltd.
Study KPL-914-C002

-
- d Abbreviated physical examination includes at minimum evaluation of vital signs, lung and heart sounds, including evaluation for pericardial rub.
 - e ECHO is required to be obtained according to the central core lab parameters and then read locally and submitted to the central core lab for separate review and analysis.
 - h Lipid panels are non-fasting and are to be drawn at a minimum of every 6months during the randomization withdrawal and LTE periods, or more frequently as needed, with mandated evaluations as detailed in the schedule of events.
 - j For women of child bearing potential - urine pregnancy testing can be repeated as needed throughout the course of the study and serum pregnancy can be drawn as needed; urine pregnancy is required to be performed at enrollment and 6 weeks after the last dose of study drug.
 - l Adverse event reporting begins following the subject providing informed consent.
 - m All procedures are to be completed prior to study drug administration.
 - o Study drug administration is once weekly with a minimum of 5 days required between doses.
 - s PK and ADA samples will be collected prior to study drug administration. PK at enrollment/baseline will be taken from ADA. As required, ADA samples will be collected at EOS, ET, and Unscheduled visits.
 - t The EORW visit serves as both the last visit of the RW period and the baseline visit of the LTE period.
 - u For all subjects, the final clinic visit of the end of RW period is to be scheduled once the End of the Randomization Withdrawal end date is announced by Sponsor. This includes subjects that are taking blinded study drug, open-label rilonacept, or who have prematurely discontinued study drug.
 - v Study drug administration to occur only after subject provides informed consent for the open-label extension period.

Table 6: Study Schedule of Activities – Long Term Extension

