- o Study drug administration is once weekly with a minimum of 5 days required between doses.
- z The MRI to occur only if the previous MRI was done longer than 6 months ago.

Table 7: Study Schedule of Activities – Supplemental Visits

Visit Name	PERICARDITIS RECURRENCE ASSESSMENT	END of TREATMENT (EOT)^x	SAFETY FOLLOW UP (SFU)^y (6 weeks post last dose)
Visit Window^b (days)	N/A	N/A	+/- 2
Visit Type	Clinic	Clinic	Clinic or TC/RN
Concomitant medications	X	X	X
Pericarditis Concomitant medications	X	X	X
Full Physical Examination ^c		X	
Abbreviated Physical Examination ^d	X		
Body weight and height	X		
12-Lead ECG	X	X	
Echo ^e	X ^e	X	
MRI (substudy only)		X ^z	
Pericardial pain (11-point NRS)	X	X	
EQ-5D	X	X	
SF-36	X	X	
ISI	X	X	
PGIPS	X	X	
PGA-PA	X	X	
Hematology, Chemistry Labs (Central)		X	
Lipid Panel (Central) ^h		X	
CRP (Local)	X		
CRP(Central)	X	X	
PK (Central)	X	X	X
ADA (Central)	X	X	X
Biomarkers (Central)	X	X	
Urine Pregnancy ^j (Local or Central)			X
Urinalysis		X	
IWRS Subject Status Update	X ^s	X	
IWRS Weight Input (pediatric only)	X		
IWRS Drug Dispensing	X		

Statistical Analysis Plan

Kiniksa Pharmaceuticals, Ltd.
Study KPL-914-C002

Visit Name	PERICARDITIS RECURRENCE ASSESSMENT	END of TREATMENT (EOT)^x	SAFETY FOLLOW UP (SFU)^y (6 weeks post last dose)
Visit Window^b (days)	N/A	N/A	+/- 2
Visit Type	Clinic	Clinic	Clinic or TC/RN
Study Drug Compliance Review	X	X	
Assessment of Pericarditis Recurrence	X	X	X
Adverse Event Reporting ^l	X	X	X

- b Scheduling of visits within visit windows requires cautious planning to ensure there is no interruption to subject evaluation and study drug treatment.
- h Lipid panels are non-fasting and are to be drawn at a minimum of every 6 months during the randomization withdrawal and LTE periods, or more frequently as needed, with mandated evaluations as detailed in the schedule of events.
- j For women of child bearing potential - urine pregnancy testing can be repeated as needed throughout the course of the study and serum pregnancy can be drawn as needed; urine pregnancy is required to be performed at enrollment and 6 weeks after the last dose of study drug.
- l Adverse event reporting begins following the subject providing informed consent.
- s PK at enrollment/baseline will be taken from ADA.
- x An EOT visit is to be conducted throughout the course of the study when a subject permanently discontinues study drug.

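### The ADA subgroups for the primary endpoint count post-randomization antibody results, which depend on arm and on recurrence, so they can show a false ADA-by-treatment difference

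*SAP*

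**What the plan says.** SAP version 2.0, Section 3.4, opens the last of its subgroups of the primary endpoint with "ADA status: ADA positive at any assessment"; the full definition is "ADA status: ADA positive at any assessment, ADA positive with neutralizing antibody at any assessment, and ADA negative at every assessment". It plans p-values, summary statistics and a forest plot; the one caveat is that the sample is probably too small for adequate power. Section 8 repeats the definition ("The following 3 categories will be used in the subgroup analysis for the primary endpoint") and begins its list with "Subjects with ADA Positive at Any Assessment". Neither section limits the status to samples taken before randomization.

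Per Section 8, ADA blood is "collected at RI baseline, RI weeks 2, 6, 12 (= RW baseline), RW week 24, end of RW/LTE baseline, and LTE week 24". Four of these times fall on or before randomization and three after it. Under Section 2.4 the LTE Week 24 sample falls after the primary data cutoff, so RW Week 24 and the end-of-RW (EORW) visit are the scheduled post-randomization samples in the primary analysis. Section 13.1 adds others. In Table 7 the ADA row is marked under "PERICARDITIS RECURRENCE ASSESSMENT", End of Treatment and Safety Follow Up, and a Table 5 footnote states "As required, ADA samples will be collected at EOS, ET, and Unscheduled visits".

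Section 2.1 gives open-label bailout rilonacept, whatever the randomized arm, to subjects whose recurrence meets the NRS and CRP criteria.

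**The concern.** Every other variable listed in Section 3.4 is a baseline or enrollment characteristic. ADA status is the only one that can change after randomization.

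Rilonacept subjects remain exposed throughout RW whether or not they recur. Placebo subjects stop at randomization and normally resume only through bailout, which follows a recurrence. The bailout criteria (NRS at least 4 and CRP at least 1 mg/dL within 7 days) match the first recurrence criterion given to the CEC in Section 5.2.1.2, so bailout is closely tied to the primary event. If re-exposure leads some subjects to form antibodies, placebo subjects with events move into the ADA-positive group and placebo subjects without events stay in the negative group. No such sorting by event occurs in the rilonacept arm. The placebo event rate then rises among positives and falls among negatives, although antibodies do nothing.

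This subgroup is read to see whether antibodies reduce efficacy, and the distortion runs the other way. The low-power caveat does not cover it, because a larger sample would not remove it.

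**Working it through.** **1. The plan's own figure.** Inputs from Section 2.3.1: one-sided alpha 0.025, power 90%, HR 0.244, placebo median 8 weeks, exponential times. Schoenfeld's formula for 1:1 allocation is

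d = (z₀.₉₇₅ + z₀.₉₀)² / [0.25 × (ln HR)²] = (1.960 + 1.282)² / [0.25 × (ln 0.244)²] = 21.1, rounded up to 22.

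Power with 22 events is 0.911. Enrollment is 50 / (1 − 0.10) = 55.6, so 56. The plan's figures are reproduced.

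**2. Simulation of the ADA rule.**
- From the SAP: exponential times, placebo median 8 weeks, HR 0.244 for every subject, 1:1 allocation, cutoff when 22/50 = 44% have an event, ADA read at RW Week 24, EORW and the recurrence visit.
- Assumed, not in the SAP: 10-35% ADA-positive by RW baseline; 20-60% conversion within 24 weeks on drug; uniform accrual over 40 weeks (20 and 60 also tried); ADA persists once positive; every placebo recurrence receives bailout; placebo subjects convert only after bailout. ADA has no effect on recurrence.
- Analysis: unstratified Cox model within each ADA group, 400,000 subjects per scenario.

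| Positive at RW baseline | Conversion in 24 weeks | HR, positive at any | HR, negative at every | Ratio |
|---|---|---|---|---|
| 10% | 20% | 0.178 | 0.260 | 0.68 |
| 10% | 40% | 0.159 | 0.284 | 0.56 |
| 10% | 60% | 0.151 | 0.318 | 0.47 |
| 20% | 20% | 0.206 | 0.260 | 0.79 |
| 20% | 40% | 0.183 | 0.282 | 0.65 |
| 20% | 60% | 0.173 | 0.317 | 0.55 |
| 35% | 20% | 0.224 | 0.260 | 0.86 |
| 35% | 40% | 0.207 | 0.279 | 0.74 |
| 35% | 60% | 0.196 | 0.315 | 0.62 |

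With status fixed at RW baseline, the HR is 0.24-0.25 in both groups in every row. With no drug effect (true HR 1.0) the planned rule gives 0.77 versus 1.11 (20-week accrual) and 0.76 versus 1.17 (60-week accrual), against 1.00-1.02 in both groups by baseline status.

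**3. What drives it** (20% positive at baseline, 40% conversion):
- No conversion after randomization: 0.243 versus 0.244.
- No bailout: 0.246 versus 0.246.
- Recurrence-visit sample dropped: 0.186 versus 0.283, essentially unchanged.
- Bailout in 70% of placebo recurrences: about 0.20 versus 0.27.
- Placebo conversion still possible for 6 weeks after withdrawal: about 0.21 versus 0.27.

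The difference therefore needs both post-randomization conversion and bailout re-exposure.

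**4. Size against noise.** In the central case the bias on the log scale is ln(0.183/0.282) = −0.43. Over the grid it runs from ln(0.86) = −0.15 to ln(0.47) = −0.76. In simulated trials of 50 subjects and 22 events, the log ratio of the two subgroup HRs has a standard deviation of about 1.0, and in 13-41% of trials at least one subgroup HR cannot be estimated.

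**The case against.** The best reply is that little hangs on this. The ADA subgroup lies outside the testing hierarchy of Section 3.3, no interaction test is planned, and at the planned size the bias is smaller than the sampling error. All of that stands and limits the weight of the point.

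The size also rests on assumed conversion rates, full bailout and no placebo conversion after withdrawal. Relaxing the last two narrows the gap without reversing it. A reader might infer that the rule must create a false difference, or would hide a real antibody effect. The SAP supports neither: without post-randomization conversion there is no bias, and so small a subgroup could rarely show an antibody effect under any definition.

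A reader might also blame the extra sample at the recurrence visit. It adds little, and the schedule footnotes place ADA sampling before study drug administration, so that sample precedes any bailout given at the visit. Subjects without recurrence are sampled at RW Week 24 and EORW as well.

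Nor is the overlap of rows an error. Positive at any assessment and negative at every assessment are mutually exclusive; the neutralizing-antibody row is a visible subset of the positives and causes no bias.

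Finally, the remedy has limits. Only Week 12 responders are randomized, and pre-randomization status cannot reveal loss of effect from antibodies formed during RW. That is true, but the planned rule cannot give an unbiased answer to that question either.

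**Conclusion.** The point holds as a correctable weakness in an exploratory analysis. The any-assessment rule makes subgroup membership depend on arm and outcome. If subjects seroconvert after randomization and placebo recurrences lead to bailout, it can make the treatment effect look better in ADA-positive than in ADA-negative subjects when there is no difference. Under the stated assumptions the size is roughly HR 0.15-0.22 versus 0.26-0.32 around a common 0.244. The direction persists under partial bailout and placebo carry-over; the magnitude depends on rates that the SAP does not supply. It should not be read as a threat to the primary result: the log-rank test, its alpha and the 22-event target are untouched.

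**What to change.** - In Sections 3.4 and 8, for the primary-endpoint subgroup p-values and forest plot, define ADA status from samples taken on or before randomization (RI baseline through RW baseline).
- Reconcile the Week 12 sample. Section 8 lists it, but the ADA row of Table 4, as it reads in the available copy, shows marks only at RI baseline, Week 2 and Week 6. A table-extraction fault may explain this. If the Week 12 sample was not planned, state the last pre-randomization sample that is used.
- Report any-assessment status, including neutralizing antibody, descriptively only, without treatment-effect p-values.

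The cost is a few lines of SAP text and one derived variable. The downside is that subjects who seroconvert only after randomization count as negative, so the subgroup cannot show loss of effect from antibodies formed during RW; the SAP should say so beside the forest plot.

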3.5. Handling of Missing Data

To the extent possible, attempts will be made to minimize the amount of missing data through measures planned in the study. Unless otherwise specified, missing data will not be imputed and only the observed data will be used in the analyses.

Additional rules for missing data imputation are provided in Section 13.2.

4. ANALYSIS SETS

4.1. Intent-to-Treat (ITT) Analysis Set

All subjects who are randomized in the RW period will be included in the Intent-to-Treat (ITT) analysis set. The primary analysis for efficacy endpoints in the RW period will be based on the ITT analysis set unless otherwise specified. Treatment comparisons for all analyses will be based on each subject's treatment assignment from randomization.

The following analysis sets are defined for the analysis of secondary endpoints:

- ITT Week 24 analysis set: All subjects randomized at least 24 weeks before data cutoff will be included. This analysis set will be used for secondary efficacy endpoints measured at week 24 in the RW period.
- ITT Week 16 analysis set: All subjects randomized at least 16 weeks before data cutoff will be included. This analysis set will be used for secondary efficacy endpoints measured at week 16 in the RW period.
- ITT Week 8 analysis set: All subjects randomized at least 8 weeks before data cutoff will be included. This analysis set will be used for secondary efficacy endpoints measured at week 8 in the RW period.

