2.3. Sample Size Calculation and Randomization

2.3.1. Sample Size Calculation

Sample size calculation is based on the primary endpoint, time to pericarditis recurrence defined as the time from randomization to the date of the first pericarditis recurrence for each subject. Time to pericarditis recurrence is assumed to follow an exponential distribution. An event of interest is defined as a subject's first adjudicated recurrence of pericarditis. The following assumptions are used in the sample size calculation using EAST 6.4.1:

- 1-sided significance level: 2.5%
- Power: 90%
- Median time to event (in weeks) in placebo: 8
- Hazard ratio (rilonacept/placebo): 0.244
- Percentage of subjects in the RI period that will not reach RW: 10%.

Given these assumptions, a total of 22 adjudicated pericarditis recurrence events is required to achieve the power. About 25 subjects per arm (a total of 50 subjects) or more will be randomized. Considering 10% of subjects in the RI period that will not reach the RW period, approximately 56 subjects will be enrolled in this study.

Subject enrollment and the pericarditis recurrence event accrual will be closely monitored during the study. The monitoring activities will be done in a blinded fashion during the RW period. If the number of subjects randomized is less than 50 and/or the time anticipated for the number of events required for the analysis of primary efficacy endpoint significantly exceeds the projected timeline, additional subjects may be enrolled and/or randomized at Kiniksa Pharmaceutical's discretion. However, at this time it is anticipated that no more than 100 subjects will be enrolled into this study.

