2.4. Timing of Analysis

The data cutoff for the primary analysis will be the end of RW period. When at least 22 adjudicated pericarditis recurrence events have occurred, end of RW period will be announced. The sites will have their subjects return to the site for the end-of-RW assessment (EORW). Data cutoff will occur after all subjects have completed this assessment. All data for this cutoff will be used in the primary analysis for efficacy and safety.

After the RW period, there will be a Long-term Extension Treatment period. An analysis will also be conducted after the end of the study. Since the data cutoff for the primary analysis will be done by the end of RW period, summary for LTE period will not be included in the primary analysis.

No interim analysis for claiming efficacy is planned. Interim safety review will be conducted by a Data Monitoring Committee (DMC). The analysis will be performed by a designated CRO. Details are in DMC charter and DMC Statistical Analysis Plan (SAP).

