5.2.2.1. Definition of Major Secondary Efficacy Endpoints in the RW Period

This section defines 3 major secondary endpoints. These endpoints will be analyzed with the ITT Week 16 analysis set. Handling of missing data due to end of RW period will be discussed in Section 5.2.2.2.

1. Proportion of subjects who maintained clinical response at Week 16 of the RW period. clinical response is defined as a weekly average of daily pericarditis pain on the 11-point NRS ≤ 2.0 and CRP level ≤ 0.5 mg/dL, and on monotherapy of randomized study drug at Week 16.

Subjects who complete 16-week of double-blinded treatment and meet the clinical response criteria at Week 16 will be considered as responders. Subjects who had recurrence, discontinued double-blinded treatment, lost to follow-up, and used bailout riloncept or rescue medications (ORT or corticosteroid) before Week 16 will be considered as non-responders.

If either weekly average of NRS or CRP is missing at week-16 assessment, the subject will be considered as a non-responder.

2. Percentage of days with pain NRS ≤ 2 in the first 16 weeks of the RW period. No or minimal pain is defined as non-missing NRS ≤ 2 .

The denominator will be 112 (=16x7) for every subject. NRS assessments after treatment termination will be included. NRS assessments while on rescue medications for pericarditis will considered not meeting this criterion. Receiving each administration of bailout riloncept will disqualify for meeting NRS ≤ 2 for 7 days. Missing values will be counted as 0 day meeting the criterion.

3. Proportion of subjects with absent or minimal pericarditis symptoms (based on the 7-point PGIPS) at Week 16 of the RW period.

Subjects who do not have the assessment due to early termination or other reasons will be considered as not meeting the criterion. Subjects who took rescue medications at the Week 16 assessment or used bailout riloncept on or before Week 16 will also be considered not meeting the criteria.

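### The ITT Week 8/16/24 sets are keyed to data cutoff rather than the end of the randomized-withdrawal period, so a few subjects closed out administratively count as failures, and the promised handling rule is missing

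*SAP*

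**What the plan says.** The references are to SAP version 2.0; version 1.0 has the same set definition, cutoff wording and cross-reference.

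- **Section 4.1:** "ITT Week 16 analysis set: All subjects randomized at least 16 weeks before data cutoff will be included". The Week 8 and Week 24 sets are built the same way.
- **Section 2.4:** once at least 22 adjudicated events have occurred, the end of the RW period is announced and subjects return for the EORW visit. "Data cutoff will occur after all subjects have completed this assessment". The same section opens by equating the data cutoff with the end of the RW period.
- **Section 13.1, Table 5:** the EORW visit has a window of 7 days either side of the announced date. Footnote t: "The EORW visit serves as both the last visit of the RW period and the baseline visit of the LTE period".
- **Section 5.2.2.1:** all three major secondary endpoints use the Week 16 set. For endpoint 1, "If either weekly average of NRS or CRP is missing at week-16 assessment, the subject will be considered as a non-responder"; stopping double-blind treatment before Week 16 also counts as non-response. Endpoint 2 divides by a fixed 112 days and gives missing days no credit. Endpoint 3 treats an absent Week 16 PGIPS, for whatever reason, as criterion not met.
- **Section 5.2.2.1 also promises:** "Handling of missing data due to end of RW period will be discussed in Section 5.2.2.2". Section 5.2.2.2 gives confidence intervals, CMH tests and an ANCOVA, and nothing on missing data.
- **Section 3.3:** all three endpoints are in the alpha-controlled family, and the first gates the other two.

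**The concern.** Membership of the Week 16 set should mean that the subject could have been observed to Week 16 of blinded treatment. Data cutoff does not secure that, because it comes after the last EORW visit while a given subject's blinded period stops at their own. Someone randomized at least 16 weeks before cutoff, but less than 16 weeks before their own EORW visit (beyond the 2-day Week 16 visit window), is in the set with no possible Week 16 assessment.

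Nothing elsewhere supplies the data. By-visit analyses use nominal visits (Section 3.1), and no rule maps EORW data to Week 16. The LTE schedule (Table 6) has no daily pain row and takes its first CRP and PGIPS at LTE Week 12. The addendum confirms that pain scores in the LTE were collected only upon recurrence. The observed-data default in Section 3.5 yields to the failure rules of Section 5.2.2.1.

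So closing the period is scored as treatment failure on alpha-controlled endpoints. It removes would-be responders mainly from the rilonacept arm, because under the planning assumptions most placebo subjects have recurred by Week 16.

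**Working it through.** **Inputs (Section 2.3.1).** "Median time to event (in weeks) in placebo: 8" weeks, exponential; "Hazard ratio (rilonacept/placebo): 0.244"; 1-sided 2.5%; 90% power; 22 events; 50 randomized 1:1; 10% not reaching RW.

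**The plan's own figures reproduce.** Events by Schoenfeld's formula: 4 × (1.960 + 1.282)² / (ln 0.244)² = 21.12, rounded up to 22; power with 22 events is 91.1%. Enrollment: 50 / 0.90 = 55.6, rounded up to 56. These are not in dispute.

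**Week 16 rates under the same assumptions**, with recurrence-free status standing in for response:
- Placebo: 0.5^(16/8) = 0.250
- Rilonacept: 0.250^0.244 = 0.713
- Difference: 46.3 points

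**Subjects in the gap.** The SAP gives neither an accrual curve nor the length of the gap. Assume 50 subjects randomized evenly over A weeks and a gap of g weeks; the number affected is 50 × g / A.

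| Gap | A = 26 | A = 52 |
|---|---|---|
| 1 week | 1.9 | 1.0 |
| 2 weeks | 3.8 | 1.9 |
| 4 weeks | 7.7 | 3.8 |

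**Whose status actually changes.** Across the two arms, (0.713 + 0.250) / 2 = 0.48 of gap subjects would have been responders; the rest fail anyway. For a 1-week gap that is 1.9 × 0.48 = 0.9 down to 1.0 × 0.48 = 0.5 subjects. Would-be responders are lost at 0.713 : 0.250, about 3 to 1, rilonacept to placebo.

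**Dilution.** If a fraction f of the set is forced to fail in both arms, the difference becomes 46.3 × (1 − f). With Week 16 sets of about 22 to 36 subjects:
- 1.9 of 22: f = 0.086, difference 42.3
- 1.0 of 36: f = 0.028, difference 45.0

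**Simulation.** Settings: 4,000 trials per scenario, the same hazards and accrual range, and RW closed at the 22nd event (or, alternatively, not before the last randomization). EORW visits were spread uniformly over 7 days either side of closure, with cutoff at the last visit. On average 0.4 to 0.9 subjects change status, the difference falls by about 1 to 4 points, and in roughly 40 to 65% of trials nobody changes status. If all EORW visits fall at closure and cutoff comes 4 weeks later, the difference is 33 to 42 points.

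**Power, illustration only.** This takes 25 per arm and the same number affected in each arm. The real Week 16 set is smaller, so compare the last two columns rather than read either as the trial's power.

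| Affected per arm | Difference if forced | Power, forced to fail | Power, excluded |
|---|---|---|---|
| 0 | 46.3 | 93.1% | 93.1% |
| 1 | 44.4 | 90.9% | 92.1% |
| 2 | 42.6 | 88.2% | 90.9% |
| 5 | 37.0 | 78.5% | 86.3% |

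**Endpoint 2.** Each unobserved week costs an affected subject at most 7 / 112 = 6.25 percentage points.

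**The case against.** The strongest reply is that the effect is small, conservative and possibly nil. Most of it stands.

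- **Scope.** A reader might infer that everyone closed out before Week 16 becomes a non-responder. The SAP does not do that: subjects randomized less than 16 weeks before cutoff are outside the set. Only the gap between a subject's own EORW visit and cutoff matters.
- **Size.** A loss of 10 points or more might be inferred. It needs a gap of about 4 weeks, which the SAP does not state; its visit window is 7 days either side. Late visits could lengthen the gap, but that is an assumption.
- **Zero case.** If randomization ended at least 16 weeks before the EORW visits, no Week 16 endpoint is affected.
- **Direction.** Membership depends on calendar time and the rule ignores arm, so it neither inflates type I error nor favors rilonacept in expectation. Chance imbalance remains possible in so small a set. The primary endpoint is untouched.
- **Endpoint 2.** The fixed denominator might be read as scoring an affected subject at zero. Only the days after EORW are lost.
- **Cutoff wording.** Section 2.4 also equates cutoff with the end of the RW period. Read as the announced date, this shrinks the gap to at most about 7 days but does not close it, because EORW visits may precede that date. The more specific sentence puts cutoff after the last visit.

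None of this answers the remaining fault: followed literally, the rules score some administrative closures as treatment failures, and the section named to deal with them is silent.

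**Conclusion.** The point holds, with limited consequences. The Week 8/16/24 sets use the wrong reference date, Section 5.2.2.1 turns the resulting missing data into failures (endpoints 1 and 3) or failing days (endpoint 2), and the promised handling is absent.

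Under the planned hazards, even accrual of 50 subjects over 26 to 52 weeks and the stated EORW window, fewer than about one subject changes status on average and the Week 16 difference falls by about 1 to 4 points from 46. A longer gap costs more; early completion of randomization makes the cost zero. All of this uses recurrence-free status as a proxy for response. The expected effect is dilution and some lost power, chiefly relevant because endpoint 1 gates the other two. The Week 8 and Week 24 endpoints share the flaw but are not alpha-controlled. This should be fixed; it does not threaten the primary result or risk a false claim.

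**What to change.** 1. **Change the reference date in Section 4.1.** Define the sets as subjects randomized at least 8, 16 or 24 weeks before the announced RW end date. That is one calendar date, independent of arm and outcome. If no administrative missingness is wanted, use the announced date minus 7 days.
2. **Settle Section 5.2.2.2.** With the announced date, state how the few subjects whose EORW visit precedes Week 16 are handled: for example, use EORW data falling within the Week 16 visit window and otherwise exclude the subject as administratively closed. With the minus-7-day date, delete the empty cross-reference.
3. **Reconcile the two cutoff statements in Section 2.4**, so that cutoff means one date.

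**Cost.** One sentence per set and one short rule. Late-randomized subjects leave the sets. The minus-7-day version drops about 1 to 2 more (50 × 1/52 = 1.0 to 50 × 1/26 = 1.9), some of whom have observed Week 16 data, so the announced date with an explicit rule is the less wasteful choice.
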